5.2 Inclusion Criteria

1. Signed Written Informed Consent

a) Written informed consent must be obtained from the subject in accordance with requirements of the study center's institutional review board (IRB) or ethics committee, prior to the initiation of any protocol-required procedures.

2. Target Population

Subject has at least 1 year history of episodic migraine (with or without aura) consistent with a diagnosis according to the International Classification of Headache Disorders, 3rd Edition⁴, including the following:

- Age of onset of migraines prior to 50 years of age.
- Migraine attacks, on average, lasting 4 72 hours if untreated.
- c) Per subject report, 4-14 migraine attacks per month within the last 3 months prior to the Screening Visit (month is defined as 4 weeks for the purpose of this protocol).
- 4 or more migraine days during 28 days in the Observation Phase.
- e) Not more than 14 *headache days* during 28 days in the Observation Phase.
- Ability to distinguish migraine attacks from tension/cluster headaches.

- g) Subjects with contraindications for use of triptans may be included provided they meet all other study entry criteria.
- Age and Reproductive Status
 - a) Male and female subjects ≥ 18 years.
 - b) Women of childbearing potential (WOCBP) and non-sterile men must be using two acceptable methods of contraception to avoid pregnancy throughout the study in such a manner that the risk of pregnancy is minimized. See Section 5.6 for the definition of WOCBP. Males with vasectomy are considered surgically sterile provided the procedure occurred greater than 6 months (24 weeks) prior to study participation.
 - c) At the Baseline Visit, WOCBP must have a negative pregnancy test (minimum sensitivity 25 IU/L or equivalent units of HCG) before dosing with study drug.
- 4. No clinically significant abnormality identified on the medical or laboratory evaluation. A subject with a clinical abnormality or laboratory parameters outside the reference range may be included only if the investigator considers the finding not clinically significant, that it will not introduce additional risk factors, nor interfere with the study procedures (not including exclusion criteria listed in Section 5.3).

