- Subject has current diagnosis of major depressive disorder requiring treatment with atypical antipsychotics, schizophrenia, bipolar disorder, or borderline personality disorder.
- o) Body mass index > 35.0 kg/m².

- History of anaphylaxis to any substance or a clinically important reaction to any drug.
- Sex and Reproductive Status
 - a) WOCBP who are unwilling or unable to use an acceptable contraceptive method or abstinence to avoid pregnancy for the entire study and for 60 days after the last dose of study drug.
 - b) Women who are pregnant or breastfeeding.
 - Women with a positive pregnancy test at screening or prior to study drug administration.
- ECG and Laboratory Test Findings
 - a) Estimated glomerular filtration rate (eGFR) according to the re-expressed abbreviated (four-variable) Modification of Diet in Renal Disease (MDRD) Study equation ≤ 30 ml/min/1.73m².
 - Abnormal ECG that in the investigator's opinion makes the subject unsuitable for a clinical trial (e.g. Corrected QT interval > 470 msec, Left Bundle Branch block)
 - c) Total serum bilirubin > 1.5 x ULN.
 - d) AST or ALT > 1.5 x ULN.
 - e) Serum albumin < 2.8 g/dL.
 - f) Neutrophil count ≤ 1000/μL (or equivalent)
 - g) HbA1c > 7.5%
- 6. Prohibited Medications
 - a) Medication for migraine prophylaxis generally considered to have efficacy, regardless of indication, taken within 30 days prior the Screening Visit (see Section 16.5 Appendix 5).
 - b) Analgesics (e.g., nonsteroidal anti-inflammatory drugs [NSAIDs] or acetaminophen) taken ≥ 15 days per month during the 3 months (12 weeks) prior to the Screening Visit.
 - c) Medication accepted for treatment of acute migraine (Section 5.5.1) for a non-migraine indication taken ≥ 15 days per month during the 3 months (12 weeks) prior to the Screening Visit.
 - Low dose aspirin (up to 100mg daily) for documented cardiovascular prophylaxis is allowed.

- d) Biologic migraine medication (such as CGRP monoclonal antibodies listed in Section 16.5 Appendix 5) taken during the 6 months (24 weeks) prior to the Screening Visit.
- e) Prohibited medication or device used during the Observation Phase (see Section 5.4).

Other Exclusion Criteria

- a) Prisoners or subjects who are involuntarily incarcerated.
- Subjects who are compulsorily detained for treatment of either a psychiatric or physical (e.g., infectious disease) illness.

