5.4 Prohibited and Restricted Concomitant Medications and Devices

All medications taken by subjects at the Screening Visit until the last study day will be documented as concomitant medications including vaccinations.

The medications and devices listed below are prohibited or restricted during the entire study, i.e., starting at the Screening Visit and through the Follow-up Week 8 Visit, unless otherwise specified.

- Medication for migraine prophylaxis generally considered to have efficacy, regardless of indication (see Section 16.5 Appendix 5). Note these are also prohibited 30 days prior to the Screening Visit (see Section 5.3), with exceptions noted for CGRP monoclonal antibodies in item 2 below and botulinum toxin injections in item 3 below.
- CGRP antagonists (monoclonal antibodies [e.g., Aimovig® or Ajovy®] or small molecule
 [e.g., Nurtec® ODT or UbrelvyTM]) other than rimegepant provided for this clinical study.
 Note that CGRP monoclonal antibodies listed in Section 16.5 Appendix 5 are also prohibited
 within 6 months (24 weeks) prior to the Screening Visit (see Section 5.3).
- Botulinum toxin injections (eg, Botox®) used for the prevention of migraine, listed in Section 16.5 Appendix 5. Note that this is also prohibited within 3 months (12 weeks) prior to the Screening Visit.
- St. John's Wort

- Ergotamine. Note the following:
 - Reporting of ergotamine use is required for the purpose of defining migraine days.
 - b. Use of ergotamine on ≥ 10 days per month on a regular basis for ≥ 3 months (≥ 12 weeks) in the year prior to the Screening Visit is also prohibited.
- Narcotics, such as opioids (e.g., morphine, codeine, oxycodone, hydrocodone) or barbiturates (e.g., butalbital). Note that use of narcotics for ≥ 4 days per month during the 3 months (12 weeks) prior to the Screening Visit is also prohibited.
- Acetaminophen or acetaminophen-containing products for non-headache indications. Note that acetaminophen as acute migraine medication as described in Section 5.5.1 is allowed during the study.
- Marijuana and all forms of ingested or inhaled cannabidiol (CBD) and THC-containing products
- Moderate to strong CYP3A4 inhibitors. If use of a moderate or strong CYP3A4 inhibitor is required, then dosing with study drug should be stopped and should not start again until 14 days after the last dose of the moderate or strong CYP3A4 inhibitor. Please see Section 16.2 Appendix 2.

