9 APPENDICES

9.1 Relevant Protocol Deviations

Relevant eligibility protocol deviations include the following categories:

- Previously treated with study drug in another multiple-dose BHV3000 study. Defined as subjects with (1) previous BHV3000 study subject identifiers from studies BHV3000-201/305/405/406/407 from the Demographics/Informed Consent CRF, and (2) who took ≥ 1 dose of study drug (e.g., rimegepant or placebo) in a multiple-dose study.
- Randomized or treated with study drug under > 1 subject identifier. These are identified from the Protocol Deviations CRF.
- Migraine history issue, defined as any of the following subcategories:
 - $0 \le 3$ or ≥ 15 migraine days per month of any pain intensity in the 3 months prior to screening
 - \circ \geq 15 headache days per month in the 3 months prior to screening.

These are based on the Migraine History CRF.

- Finding out of range during pretreatment, defined any as any of the following subcategories:
 - o Females with a positive pregnancy test (see Section 6.4.2)
 - Estimated glomerular filtration rate (eGFR) according to the re-expressed abbreviated (4-variable) Modification of Diet in Renal Disease (MDRD) Study equation ≤ 40 mL/min/1.73m², if originally consented to Protocol Version 4 or lower *
 - eGFR according to the re-expressed abbreviated (4-variable) MDRD Study equation < 30 mL/min/1.73m², if originally consented to Protocol Version 5 or higher *
 - o BMI \geq 33 kg/m², if originally consented to Protocol Version 4 or lower *
 - o BMI > 35 kg/m², if originally consented to Protocol Version 5 or higher *
 - C-SSRS suicidal ideation with active intent or plan to act, or suicidal behavior present during pretreatment. Defined as having a "yes" response to any of the following C-SSRS questions:
 - Suicidal ideation question 4 (active suicidal ideation with some intent to act, without specific) or 5 (active suicidal ideation with specific plan and intent)
 - Suicidal behavior question 1 (actual attempt), 3 (interrupted attempt), 4 (aborted attempt), 5 (preparatory acts or behavior), or 6 (suicidal behavior).

For the subcategories marked with "*", all nonmissing values during the pretreatment analysis period must meet the deviation criteria in order to be considered a deviation.

- Efficacy data issue during the first 28 days of the OP, defined as any of the following subcategories:
 - \circ \leq 3 migraine days
 - ≥ 15 headache days

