 - \circ \leq 23 days of eDiary efficacy data (see Sections 6.2.6.2 and 9.2.2).

These are assessed during the 28-day OP analysis period (see Section 7.2). Migraine days and headache days are absolute, not prorated to 28 days per month (see Sections 9.2.5 and 9.2.6), and of total pain intensity.

Relevant subject management protocol deviations include the following categories:

- Randomization stratum discrepancies between IWRS and actual data, defined as any of the following subcategories:
 - IWRS randomization stratum of yes, but no use of nonstudy previous medication for migraine prevention generally considered to have efficacy
 - IWRS randomization stratum of no, but use of nonstudy previous medication for migraine prevention generally considered to have efficacy.

See Section 6.2.5.4 for the definition of nonstudy medication for migraine prevention generally considered to have efficacy.

- DB study drug dosing noncompliance, defined as any of the following subcategories (see Section 6.2.6.2):
 - DB study drug taken but not randomized
 - DB tablet count compliance < 80% from DB study drug start to later of last scheduled DBT Phase visit or DB study drug end/OL rimegepant start
 - > 1 DB tablet taken on any 1 day
 - Incorrect DB study drug taken
- OL rimegepant dosing noncompliance, defined as any of the following subcategories (see Section 6.2.6.2):
 - o OL rimegepant tablet count compliance < 80% from OL rimegepant start to later of last scheduled OLE Phase visit or OL rimegepant end
 - > 1 OL rimegepant tablet taken on any 1 day
 - OL rimegepant start on or before DB study drug end
 - o OL rimegepant taken but DB study drug never taken
- eDiary usage compliance < 80% from DB study drug start to later of last scheduled DBT Phase visit or DB study drug end (see Section 6.2.6.2)
- Prohibited nonstudy medications taken on or after informed consent (or otherwise specified), defined as any of the following subcategories:

- Atypical antipsychotic, divalproex, valproic acid, or valproate #
- Ergotamine
- Lamotrigine
- Medication for migraine prevention generally considered to have efficacy or prophylactic migraine medication taken up to 30 days before informed consent or afterward (see Sections 6.2.5.4 and 6.2.6.3) #
- Narcotic (barbiturate or opioid) #
- Select moderate or strong cytochrome P450 3A4 (CYP3A4) inducer #
- Select strong CYP3A4 inhibitor #.

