For the subcategories marked with "#", preferred names are displayed alphabetically as additional subcategories. Medications taken up to X days before a reference date or afterward are defined as those with imputed medication start date or imputed end date \geq reference date -X. Refer to the Core SAP for additional details about prohibited nonstudy medications.

The IWRS randomization date is the reference date for "randomization". If the IWRS randomization date is missing, then the study drug start date is used.

The protocol version to which subjects originally consented is determined from the Demographics/Informed Consent CRF.

9.2 eDiary Efficacy

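### The programmed deviation table in SAP 9.1 under-counts breaches of the biologic wash-out (exclusion 6d) and of the lower bound on migraine attacks (inclusion 2c)

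*SAP*

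**What the plan says.** **Preventive medication.** SAP 9.1, in its list of prohibited nonstudy medications, has a single row for preventives: "Medication for migraine prevention generally considered to have efficacy or prophylactic migraine medication taken up to 30 days before informed consent or afterward". The same section explains that a medication counts as taken within the look-back when its "imputed medication start date or imputed end date" falls on or after the reference date minus the stated number of days.

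The protocol does not treat all preventives alike:

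- Exclusion 6a (Section 5.3) sets the general rule: "Medication for migraine prophylaxis generally considered to have efficacy, regardless of indication, taken within 30 days prior the Screening Visit".
- Exclusion 6d sets a longer one for biologic migraine medication, such as CGRP antibodies: "taken during the 6 months (24 weeks) prior to the Screening Visit".
- Section 5.4 item 1 repeats the 30-day rule but carves out CGRP antibodies (item 2) and botulinum toxin (item 3). Item 3 says of botulinum toxin: "Note that this is also prohibited within 3 months (12 weeks) prior to the Screening Visit".

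**Migraine history.** Inclusion 2c (Section 5.2) reads: "Per subject report, 4-14 migraine attacks per month within the last 3 months prior to the Screening Visit". The matching flag in SAP 9.1 fires at 3 or fewer, or 15 or more, "migraine days per month of any pain intensity in the 3 months prior to screening", taken from the Migraine History CRF. A second flag covers 15 or more headache days per month.

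**Reporting.** SAP 6.2.4.1 tabulates these programmed deviations and by default prints listed rows even when the count is 0. SAP 6.2.4.2 adds a by-subject listing of deviations that sites marked as significant, with the inclusion or exclusion number.

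**The concern.** The deviation table is where a reader of the study report checks whether the randomized population met the entry criteria. Two of its rules test something other than the criterion they stand next to. The wash-out rule is shorter than the protocol's for biologics, and the history rule uses a different unit.

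The biologic gap is the more relevant clinically. Residual effect of a recent long-acting preventive could lower the Observation Phase migraine-day count, which is both the reference value and the covariate for the primary endpoint (Protocol 9.3.1.1). Prior preventive use will be common, because the cap on treatment-naïve subjects is meant to leave at least 70% treatment-experienced (Protocol 1.5.1). That category covers any use before consent, so it does not show how many subjects took a biologic inside the barred window.

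Alignment with the protocol is also a standard the SAP already applies in this section. Its eGFR and BMI flags are set separately according to the protocol version each subject consented to.

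**Working it through.** The plan gives no figure on this point to reproduce. The check compares the rules and counts what falls between them.

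**1. Look-back windows.** Consent and Screening are taken as the same day (assumption; the SAP counts from consent, the protocol from the Screening Visit). Days not flagged = protocol window − 30.

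| Medication | Protocol source | Protocol window | SAP window | Not flagged | Share |
|---|---|---|---|---|---|
| Preventives in general | Exclusion 6a | 30 days | 30 days | 0 | 0% |
| Biologics | Exclusion 6d | 24 × 7 = 168 days | 30 days | 168 − 30 = 138 (days 31–168) | 138/168 = 82% |
| Botulinum toxin, if 5.4 item 3 governs | Section 5.4 item 3 | 12 × 7 = 84 days | 30 days | 84 − 30 = 54 (days 31–84) | 54/84 = 64% |
| Botulinum toxin, if 6a governs | Exclusion 6a with Appendix 5 | 30 days | 30 days | 0 | 0% |

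The botulinum toxin gap is therefore 0 or 54 days, depending on how the protocol passages are reconciled. Appendix 5 lists onabotulinumtoxinA, so 6a reaches it with a 30-day window, while Section 5.4 item 3 gives 12 weeks.

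None of the categories under eligibility deviations in SAP 9.1 covers medication wash-out, so no other row in that section picks up the biologic breach.

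**2. Attacks against days, low end.** Inclusion 2b allows untreated attacks of 4 to 72 hours. A 72-hour attack can touch up to 4 calendar days (assumption: it starts part-way through a day). With *a* attacks, migraine days then run from *a* to 4*a*. The SAP flag is silent from 4 to 14 days.

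- 1 attack: 1 to 4 days; 4 escapes.
- 2 attacks: 2 to 8 days; 4 to 8 escape.
- 3 attacks: 3 to 12 days; 4 to 12 escape.

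Each of these subjects is below the lower bound of 2c and is not flagged.

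**3. Attacks against days, high end.** Under Protocol Appendix 3, a recurrence within 48 hours of the start of an attack belongs to the same attack. At most 28 × 24 / 48 = 14 attacks then fit in a month, so exceeding 14 is essentially not possible on that definition (assumption: the same definition is applied to recalled history). A subject with 15 or more migraine days has at least 15 headache days and breaches exclusion 1b in any case. The mismatch therefore hides breaches only at the low end.

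**4. Effect on the analyses.** SAP 4.1 defines the DBT efficacy and migraine analysis sets by randomization, dosing and eDiary data. None of the 9.1 flags enters those definitions.

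**The case against.** The strongest case against has five parts.

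- **Other reporting routes.** A reader might infer that these breaches will be reported as absent, or that the table will show zero for them. The documents do not support that. SAP 6.2.4.1 prints zeros only for rows that exist, and there is no 24-week row. A breach that a site marks as significant appears in the 6.2.4.2 listing with its criterion number. Nonstudy medications are listed by subject with prophylactics identified (6.2.6.3), and migraine history is also listed (6.2.5). This stands, and it limits the point to under-counting in one programmed table. The listings are only a partial substitute: the first depends on the site noticing and marking the breach, and the others leave the reader to find it by hand.
- **A selected set.** SAP 9.1 does not try to cover every criterion; it has no rows for bilirubin, ALT/AST, HbA1c or albumin. The preventive row also sits under subject management, not eligibility. That is fair, and leaving 6d out would be a defensible choice if stated. As written, a row that covers preventives in general invites the reader to think the wash-outs were checked.
- **Botulinum toxin.** The 12-week window is in Section 5.4, not in the exclusion list, and 6a gives 30 days. This stands: it is an inconsistency within the protocol, and the 64% holds only if item 3 governs.
- **Unseen documents.** The Core SAP is cited for further detail on prohibited medications, and the Migraine History CRF is not supplied. Either could narrow the gap. The study SAP nevertheless states 30 days without exception.
- **No inferential effect.** A reader might infer that the primary result is at risk. The analysis sets do not use these rules, so the primary analysis and power are unchanged.

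**Conclusion.** The point holds as a minor error in a reporting rule. As written, the programmed table does not count biologic use last recorded 31 to 168 days before consent, nor subjects with 3 or fewer attacks but 4 or more migraine days per month. The size is 138 of 168 barred days for biologics. For migraine history it is the low-end combinations of 1 to 3 attacks with 4 to 12 days. The percentages describe calendar time, not subjects, deviations or bias, and the number of subjects affected is unknown.

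This rests on three further assumptions beyond those given in the working: the sponsor's medication file (SAP 6.2.5.4) includes the biologics that Appendix 5 names; the Core SAP does not already add a longer look-back; and the date imputation, also held in the Core SAP, does not move a medication date into the 30-day window.

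**What to change.** In SAP 9.1:

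1. Split the preventive row. Keep 30 days for preventives in general, and use the exclusion 6d window (24 weeks before Screening) for biologic migraine medication.
2. Have the sponsor reconcile exclusion 6a with Appendix 5 against Section 5.4 item 3 for botulinum toxin, and program whichever window results.
3. Base the lower-bound migraine-history flag on attacks per month if the Migraine History CRF collects them. Keep the flag for 15 or more headache days. If the CRF holds only days, footnote the row to say that inclusion 2c was not tested directly.
4. Confirm that the revised rules agree with the Core SAP.

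The cost is a few lines of text and minor programming, provided the CRF data exist. The reported deviation count may rise.

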9.2.1 Efficacy Parameters

On a given day, subjects use the eDiary to provide responses to the following efficacy parameters occurring yesterday:

- Headache (yes, no)
- If the response to headache is "yes", then responses to the following pain features and associated symptoms are collected:
 - o Lasts at least 30 minutes (yes, no)
 - o Pain intensity (mild, moderate, severe)
 - Unilateral (yes, no)
 - o Pulsating (yes, no)
 - Worsen or avoid physical activity (yes, no)
 - o Nausea (yes, no)
 - Vomiting (yes, no)
 - o Photophobia (yes, no)
 - o Phonophobia (yes, no)

- Aura (yes, no)
- If the response to headache or aura is "yes", then the responses to the following parameters about taking medications to treat headache or aura are collected:
 - Triptan (yes, no)
 - o Ergotamine (yes, no)
 - Other medication (yes, no).

These efficacy parameters are collected together as a set with the same eDiary finding date/time for a subject. It is expected that subjects have only 1 set of efficacy parameters collected on a given eDiary finding date. Handling of multiple sets on the same date are discussed in subsequent sections.

9.2.2 eDiary Efficacy Data Day

A day of eDiary efficacy data is defined as any complete eDiary efficacy date (see Section 7.1).

9.2.3 Acute Migraine Medication Day

An acute migraine medication day is defined as either (1) or (2):

- 1) Acute migraine-specific medication day (see Section 9.2.4)
- 2) Migraine day (see Section 9.2.5) with a "yes" response to the question about taking other medications to treat headache or aura.

Thus, acute migraine medication days are a subset of migraine days (see Section 9.2.5). If there are multiple sets of efficacy parameters on the same finding date, then data from all sets are used cumulatively to assess acute migraine medication day status on that day, regardless of finding time. For example, if a subject has both "yes" and "no" responses to the question about taking triptan on that day, then the subject is considered to have taken acute migraine medication on that day.

9.2.4 Acute Migraine-Specific Medication Day

An acute migraine-specific medication day is defined as a day of eDiary efficacy data with a "yes" response to either of the 2 questions about taking triptan or ergotamine to treat headache or aura.

Thus, acute migraine-specific medication days are a subset of acute migraine medication days and migraine days (see Sections 9.2.3 and 9.2.5, respectively). If there are multiple sets of efficacy parameters on the same finding date, then data from all sets are used cumulatively to assess acute migraine-specific medication day status on that day, regardless of finding time.

